9.3 Additional Efficacy Analyses

Secondary Analysis of the Primary Efficacy Variables

Analysis of covariance (ANCOVA) analyses will be carried out on change from baseline to final UDysRS total score. The ANCOVA model will contain treatment and country as the main effects and baseline score as the covariate. Sensitivity analyses will be carried out on the above variables with the same ANCOVA model using all randomized subjects. In this analysis, Baseline Observation Carried Forward (BOCF) will be applied to subjects who do not have post-randomization assessment of UDysRS.

Analysis of Secondary Efficacy Variables

The MMRM model and the descriptive statistic summary described for the UDysRS total score will also be used to evaluate the change from baseline to Week 12 in each of the following efficacy endpoints (with the exception of the CGI-C, which the score itself shows the changes):

- "ON" time without troublesome dyskinesia as measured by the PD Diary
- Parkinson's Disease Questionaire-8 (PDQ-8) summary index
- Clinical Global Impression of Change (CGI-C) Score
- UPDRS Part II Score
- "OFF" time as measured by the PD Diary
- **UPDRS** Part III Score

PD Diary variables will be normalized to a 16 hour awake time and the time recorded by the subject on the 3 diaries completed prior to each visit will be averaged.

For CGI-C, an ANCOVA model containing treatment and country as the main effects and baseline CGI-S as covariate will be carried out.

"ON" time without troublesome dyskinesia as measured by the PD Diary, PDQ-8 summary index, CGI-C score, UPDRS Part II and Part III score, and "OFF" time as measured by the PD Diary are key secondary endpoints. If the primary efficacy variable is statistically significant, each of the secondary variables will be tested using the fixed sequence above as a gatekeeping procedure and at α level of 0.050. Testing will cease at the point that a secondary variable fails to demonstrate statistical significance.

All secondary efficacy variables will be summarized by the number of subjects with nonmissing data, mean, standard deviation, median, minimum and maximum.

Analysis of Additional Efficacy and Health Variables

Efficacy will also be assessed using the following additional measures:

- UDysRS Historical Score, Objective Score and Parts 1 through 4 Scores
- "ON" time with troublesome dyskinesia and "ON" time without dyskinesia as measured by the PD Diary
- mAIMS

Health outcomes will also be assessed using the following additional measures:

- King's PD Pain Scale
- Percentage (%) of CGI-C responders (response of "minimally improved," "much improved" or "very much improved")

Continuous endpoints will be analyzed with the same MMRM model as the primary analysis. Categorical endpoints will be analyzed with a Fisher's exact test.

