Unless otherwise specified, all efficacy analyses will be performed on the ITT dataset and comparisons between the OMT and LCIG treatment groups will be performed with twosided tests at the significance level of 0.050.

8.1.3.1 **Primary Efficacy Analysis**

The primary efficacy variable is the mean change from baseline to Week 12 for the UDysRS total score.

UDysRS Total Score

The UDysRS was developed to evaluate dyskinesia in Parkinson's disease. It contains two primary sections with 26 questions:

Historical [Part 1 (On-Dyskinesia) and Part 2 (Off-Dystonia)]

Objective [Part 3 (Impairment) and Part 4 (Disability)]

Part 1 contains 11 questions about the on time dyskinesia and the impact of on-dyskinesia on experiences of daily living. Part 2 contains 4 questions of off-dystonia rating. Part 3 contains 7 questions about objective evaluation of dyskinesia impairment and Part 4 contains 4 questions regarding dyskinesia disability. Each question is scored with respect to severity, which is rated on a scale where 0 = normal, 1 = slight, 2 = mild, 3 = moderateand 4 = severe. The UDysRS total score is obtained by summing the item scores, ranging from 0 to 104.

Primary Analysis Model

The primary efficacy analysis model is a likelihood-based mixed-effects model repeated measures (MMRM) analysis of the change from baseline for each post-baseline observation using all observed data. The model will include fixed, categorical effects for treatment, country, visit, and treatment-by-visit interaction, with continuous fixed covariates for baseline score and the baseline score-by-visit interaction. The primary comparison will be the contrast between LCIG and OMT treatment at the Week 12 Visit.

Additional Analysis of the Primary Efficacy Variable

EudraCT 2016-001403-23

Analysis of covariance (ANCOVA) analyses will be carried out on change from baseline to final UDysRS total score. The ANCOVA model will contain treatment and country as the main effects and baseline score as the covariate.

The ITT dataset will not include subjects randomized to LCIG who prematurely discontinue before receiving their first LCIG infusion. To evaluate the impact of not including these subjects in the primary efficacy analysis, a sensitivity analyses will be carried out with the same ANCOVA model using all randomized subjects. In this analysis, Baseline Observation Carried Forward (BOCF) will be applied to subjects who do not have a post-randomization assessment of UDysRS.

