The final visit for PD Diary variables for the OMT group will be the average of the last 3 valid diaries that are after the day of randomization during the 12-week Treatment Period. The final visit for PD Diary variables for the LCIG group will be the average of the last 3 valid diaries that are after the date of the first LCIG infusion following PEG-J placement and on or before the date of the last LCIG infusion during the 12-week

Treatment Period. The final visit for efficacy and health outcome measure, other than PD Diary variables, for the OMT group will be defined as the last non-missing observation that is after the day of randomization during the 12-week Treatment Period. The final visit for efficacy and health outcome measures, other than PD Diary variables, for the LCIG group will be defined as the last non-missing observation that is after the date of the first LCIG infusion following PEG-J placement and no more than 1 day after the last LCIG infusion during the 12-week Treatment Period.

For subjects who discontinue LCIG treatment during the 12-week Treatment Period or complete the 12-week Treatment Period but not going to transit to commercial product, the final visit for safety assessments will be defined based on the final removal of all LCIG devices and will be the last non-missing observation that is after the date and time of the first LCIG tube (NJ or PEG-J) placement procedure and no more than 1 day after the final removal of all LCIG tubes. For subjects who transit to commercial product, the final visit will be the last non-missing observation during the 12-week Treatment Period in the database. Safety assessments on the date of the first PEG-J placement procedure that do not have a time of assessment or sample collection recorded will be assumed to be post-procedure. For subjects in the OMT group, the final visit for safety assessments will be defined as the last non-missing observation that is after the day of randomization during the 12-week Treatment Period.

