9.0 Efficacy and Health Outcome Analysis

9.1 **General Considerations**

This is a randomized open-label study. Unless otherwise specified, statistical tests will be two-sided and the null hypothesis will be rejected at the significance level of $\alpha = 0.050$. *P* values will be rounded to 3 decimal places before assessing statistical significance. Unless noted otherwise, all analyses will be performed with the Intent-to-Treat Dataset. Missing data will not be imputed unless otherwise specified.

9.2 **Primary Efficacy Analysis**

UDysRS Total Score

The UDysRS was developed to evaluate dyskinesia in Parkinson's disease. It contains two primary sections with 26 questions:

Historical [Part 1 (On-Dyskinesia) and Part 2 (Off-Dystonia)]

Objective [Part 3 (Impairment) and Part 4 (Disability)]

Part 1 contains 11 questions about the on time dyskinesia and the impact of on-dyskinesia on experiences of daily living. Part 2 contains 4 questions of off-dystonia rating. Part 3 contains 7 questions about objective evaluation of dyskinesia impairment and Part 4 contains 4 questions regarding dyskinesia disability. Each question is scored with respect to severity, which is rated on a scale where 0 = normal, 1 = slight, 2 = mild, 3 = moderate

and 4 = severe. The UDysRS total score is obtained by summing the item scores, ranging from 0 to 104.

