9.6 Efficacy Subgroup Analysis

To determine if the following factors have an impact on the response to treatment, subgroup analyses will be conducted on the change from baseline to final visit on the UDysRS total score:

- Gender
- Age category ($< 65, \ge 65$)
- Duration of Parkinson's disease (< 10 years, \geq 10 years)
- Total daily dose of levodopa (< 1250 mg, ≥ 1250 mg) at the end of initial LCIG titration for the LCIG group and in the first set of dosing diary for the OMT group
- Number of anti-PD medications other than levodopa taken at any time during the week prior to randomization (0 or 1, 2 or more)

The subgroup analyses will be performed using an ANCOVA model contain treatment, country, and subgroup as main effects, treatment by subgroup interaction, and baseline score as the covariate. The LS mean change for each stratum of the subgroup with associated 95% confidence interval will be presented.

The descriptive statistic summary described for the UDysRS total scores will also be prepared for each subgroup stratum.

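### The supportive ANCOVA and the five subgroup analyses of UDysRS carry an early stopper's last score forward, so in general they neither estimate the Week 12 contrast nor test the primary model's missing-data assumption

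*SAP*

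**What the plan says.** - **Primary test.** SAP 9.2 compares LCIG with OMT at Week 12 in an MMRM. The general rule in SAP 9.1 is "Missing data will not be imputed unless otherwise specified".
- **Supportive ANCOVA.** SAP 9.3: "Analysis of covariance (ANCOVA) analyses will be carried out on change from baseline to final UDysRS total score". Protocol 8.1.3.1 specifies the same endpoint: "carried out on change from baseline to final UDysRS total score".
- **Meaning of *final*.** Under SAP 6.3, the final visit "for the OMT group will be defined as the last non-missing observation that is after the day of randomization during the 12-week Treatment Period". For LCIG the rule reads "last non-missing observation that is after the date of the first LCIG infusion following PEG-J placement and no more than 1 day after", where the one-day limit is counted from when infusion ended.
- **Subgroups.** SAP 9.6: "subgroup analyses will be conducted on the change from baseline to final visit on the UDysRS total score". The factors are gender, age, disease duration, levodopa dose and number of other anti-PD medications.
- **All-randomized version.** SAP 9.3 adds that "Baseline Observation Carried Forward (BOCF) will be applied to subjects who do not have post-randomization assessment of UDysRS". Everyone else keeps the last score.
- **Promised analyses.** Protocol 8.1.3.3 assumes missingness at random. To examine this it commits to a completer MMRM and to further missing-data sensitivity analyses that the SAP is to describe. The SAP describes neither, while SAP 12.0 declares no change of analysis from the protocol.

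**The concern.** The *final* rule is last observation carried forward, although the SAP does not call it that or present it as imputation. Early and Week 12 scores are pooled as if they were the same outcome.

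The design gives reasons why they may differ. Protocol 5.1.2.2 requires the Week 2 assessments even while titration continues, and the protocol synopsis allows LCIG dose adjustment up to Day 28. An early on-LCIG score need not equal what the subject would have had at Week 12 on LCIG. Nor need it equal the subject's Week 12 state after stopping.

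At stake is interpretation. With the promised missing-data analyses absent from the SAP, the final-score ANCOVA and its BOCF variant are the only planned alternatives to the primary MMRM. If they agree with it, the missing-at-random assumption has not been tested. If they disagree, the cause could be missing data or simply a different mix of visits. The planned subgroup estimates rest on the same endpoint.

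**Working it through.** **1. The plan's own figure.** Inputs from SAP 4.3: difference 10, SD 12, two-sided 0.050, 27 per group. Standard error = 12 × √(2/27) = 3.27; noncentrality = 10/3.27 = 3.06 on 52 degrees of freedom; two-sample t-test power = 85.2%. Allowing for 10%, 27/0.9 = 30 per arm, 60 in total. The stated figures reproduce.

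**2. Whose score is carried forward.**
- *Early stoppers with a qualifying score.* The SAP 6.5 windows place an assessment before Day 71 in an earlier visit, so the MMRM does not treat it as Week 12. SAP 6.3 nevertheless makes it *final*.
- *Completers with an incomplete Week 12 form.* Under SAP 9.4, Table 1, one missing item of the 26 voids the total, and the previous visit's total becomes *final*.
- *Not affected.* Subjects with no post-baseline score have nothing to carry forward. They contribute nothing to the ITT ANCOVA and receive BOCF in the all-randomized version.

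**3. Size, as an illustration.** Only the 10-point effect comes from the documents. Assumptions: a fraction f of LCIG subjects stop, spread evenly after Weeks 2, 4 and 8; stoppers lose all benefit by Week 12; there is no stopping in OMT. Let s be the mean share of the full effect present at the last visit.

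- On treatment = 10
- As assigned = 10 × (1 − f)
- Carry-forward = 10 × [(1 − f) + f × s]

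| Share at Weeks 2 / 4 / 8 | s | f = 10% | f = 20% |
|---|---|---|---|
| 0.2 / 0.5 / 0.8 | 0.5 | 10 × (0.9 + 0.05) = 9.5 | 10 × (0.8 + 0.10) = 9.0 |
| 0.4 / 0.7 / 1.0 | 0.7 | 10 × (0.9 + 0.07) = 9.7 | 10 × (0.8 + 0.14) = 9.4 |
| 1.0 / 1.0 / 1.0 | 1.0 | 10.0 | 10.0 |
| As assigned | – | 9.0 | 8.0 |

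The excess over the as-assigned effect is 10 × f × s, from 0.5 (f = 0.1, s = 0.5) to 2.0 (f = 0.2, s = 1). The shortfall against the on-treatment effect is 10 × f × (1 − s), from 0 to 1.0.

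The range is not a bound. If all of a 20% loss fell after Week 2 with 40% of the effect present, carry-forward would give 10 × (0.8 + 0.2 × 0.4) = 8.8.

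**The case against.** The strongest reply is that little depends on these analyses. The primary test and the fixed sequence do not use *final*, and the subgroup models lie outside that sequence. This stands.

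The onset assumption can also be challenged. Titration is planned to take about two weeks, and Protocol 3.0 reports an OFF-time benefit evident by Week 4 that persisted. This stands in part: it concerns OFF time rather than UDysRS, but it makes the slow profile in the first row of the table the less likely end. A shift of 0.5-2.0 points is also only about 0.15-0.6 of the 3.27-point standard error.

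It can also be said that Protocol 8.1.3.1 gives the all-randomized ANCOVA a narrower purpose, namely to gauge the exclusion of never-infused LCIG subjects. That is correct, and it is why this ANCOVA cannot stand in for the missing-data analyses promised in Protocol 8.1.3.3.

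A reader might infer more than the documents support:
- *That the final-score analyses can never match either effect.* If the effect is flat from Week 2, carry-forward equals the on-treatment effect.
- *That every dropout is carried forward.* This needs at least one qualifying post-baseline score.
- *That the analyses are biased toward LCIG.* This holds only against an as-assigned effect, which the plan does not define. Against the on-treatment effect the illustrated values are equal or lower.
- *That the 10% in SAP 4.3 is a stopping rate.* It counts subjects with no post-randomization efficacy assessment.

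**Conclusion.** The point holds for the supportive ANCOVA and the five subgroup analyses, and follows from the SAP's own definitions. Whenever subjects stop early, or Week 12 totals are missing, and the effect changes after the last score, these analyses do not in general estimate the primary Week 12 contrast. They also cannot serve as a check of missingness at random.

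A reader might conclude that the primary result is compromised. The documents do not support that, because the primary MMRM and the gatekeeping do not use the carried-forward score.

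The size rests on assumed stopping of 10-20%, even timing, full loss of benefit and an assumed onset profile. On those terms carry-forward gives 9.0-10.0 points, against 10.0 on treatment and 9.0 or 8.0 as assigned. With little stopping, or an early plateau and an on-treatment question, the discrepancy is small or nil.

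**What to change.** 1. **SAP 9.3, add.** As the main missing-data sensitivity analysis promised in Protocol 8.1.3.3, specify an ANCOVA of the Week 12 change after multiple imputation in all randomized subjects. Impute LCIG stoppers and never-infused LCIG subjects from the OMT profile, which targets the as-assigned effect. The ITT dataset would not do for this, because it leaves out LCIG subjects never dosed through PEG-J.
2. **SAP 9.3, add** the promised completer MMRM for the primary and secondary variables.
3. **SAP 9.3, keep** the final-score ANCOVA, since the protocol specifies it and deleting it from the SAP alone would create a contradiction. Label it as last observation carried forward and supportive only.
4. **SAP 9.6, change the endpoint.** Apply the existing subgroup ANCOVA (treatment, country, subgroup, treatment-by-subgroup, baseline) to the Week 12 change, imputed where missing, and state the imputation rule. A repeated-measures model with a treatment-by-subgroup-by-visit term is not advised: with about 60 subjects in 6-8 countries it would be fragile.

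The cost is SAP text, modest programming and slightly wider intervals. No new data are needed.

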9.4 Calculation of Efficacy and Health Outcome Variable

The primary and secondary efficacy variables derived from the above measures are presented in Table 1.

Primary and Secondary Efficacy Variables, and Derivations Table 1.

Instrument	Efficacy Variable	Derivation	Range/Direction
UDysRS: 26 questions, Part 1 (Questions 1 – 11),	Part 1 score	Sum of Questions 1 – 11	0 – 44/lower value desirable
Part 2 (Questions $12 - 15$), Part 3 (Questions $16 - 22$), and Part 4 (Questions $23 - 26$) All questions are	Part 2 score	Sum of Questions $12 - 15$	0 - 16/lower value desirable
5-point (0 – 4). There is no imputation of missing	Part 3 score	Sum of Questions 16 – 22	0 - 28/lower value desirable
responses. If one or more item scores are missing, the	Part 4 score	Sum of Questions 23 – 26	0 - 16/lower value desirable
total score and respective domain score will not be calculated.	Historical score	Sum of Part 1 score and Part 2 score	0 – 60/lower value desirable
	Objective score	Sum of Part 3 score and Part 4 score	0 - 44/lower value desirable
	Total score	Sum of Part 1, Part 2, Part 3, and Part 4 scores	0 - 104/lower value desirable
PD Diary: 48 entries each diary day starting at 6:00 am and goes thru 6:00 am on the following chronological day, each represents 0.5 hour. Subjects were instructed	Normalized "ON" time without troublesome dyskinesia	(Absolute "On" time without dyskinesia + Absolute "On" time with non-troublesome dyskinesia)/Daily awake time * 16	0 – 16 hours/higher value desirable
to record whether "Asleep," "Off," "On without Averimenta ""On with non-tranhecome dvskimesia" or	Normalized "OFF" time	Absolute "Off" time/Daily awake time * 16	0 – 16 hours/lower value desirable
The provided structure of the provided stru	Normalized "ON" time with troublesome dyskinesia	Absolute "On" time with troublesome dyskinesia/Daily awake time * 16	0 – 16 hours/lower value desirable
without dyskinesia," "On with non-troublesome dyskinesia" or "On with troublesome dyskinesia."	Normalized "ON" time without dyskinesia	Absolute "On" time without dyskinesia/Daily awake time * 16	0 - 16 hours/higher value desirable
The "Off" and various "On" times are normalized to 16-hour awake period based a typical person's day.			
Only diaries with at least 12 hours of daily awake time will be considered valid and used in the analysis.			

30

Primary and Secondary Efficacy Variables, and Derivations (Continued) Table 1.

Instrument	Efficacy Variable	Derivation	Range/Direction
PDQ-8: 8 question including the mobility, activities of daily living, emotional well-being, stigma, social support, cognition, communication, bodily discomfort. 5-point scale: 0 = Never, 1 = Occasionally, 2 = Sometimes, 3 = Often, 4 = Always (or cannot do at all, if applicable).	PDQ-8 Summary Index (PDQ-SI)	Sum of each question divided by 32 and multiplied by 100. The PDQ-8 total score will be calculated as long as at least 7 questions have been answered. Missing values in a question will be replaced by the patient population's mean of the question, and rounded to an integer.	0 – 100/lower value desirable
CGI-C: 7-point scale $(1 = \text{very much improved}, 2 = \text{much improved}, 3 = \text{minimally improved}, 4 = no change, 5 = \text{minimally worse}, 6 = \text{much worse}, 7 = \text{very much worse})$	CGI-C score	7-point score as collected	1 – 7/lower score desirable
UPDRS: 42 questions, Part I (Questions 1 – 4), Part II (Questions 5 – 17), Part III (Questions 18 – 31), and Part IV (Questions 32 – 42). Questions 35 – 38 and 40 – 42 are 2-point (0 and 1), all other questions are 5-point (0 – 4).	Part II score	Sum of Questions 5 – 17. Part II score will be calculated as long as at least 12 questions have been answered. If 1 answer is missing the Part II score will be calculated by multiplying the sum of questions answered by the ratio of the total number of Part II questions to the number of questions answered.	0 – 52/lower value desirable
	Part III score	Sum of Questions 18 – 31 with Questions 20 – 26 apply to multiple body parts, resulting in 27 answers total. Part III score will be calculated as long as at least 23 answers have been recorded. If 4 or fewer answers are missing the Part III score will be calculated by multiplying the sum of the answers provided by the ratio of the total number of Part III answers provided.	0 – 108/lower value desirable

31

Primary and Secondary Efficacy Variables, and Derivations (Continued) Table 1.

Instrument	Efficacy Variable	Derivation	Range/Direction
mAIMS: 6 questions, all questions are 5 points $(0 - 4)$. There is no imputation of missing responses.	mAIMS score	Sum of Questions 1 – 6	0 – 24/lower value desirable
 King's PD Pain Scale (KPPS): 14 items addressing the following 7 domains (musculoskeletal pain, chronic pain, fluctuation-related pain, nocturnal pain, oro-facial pain, discoloration, oedema/swelling, radicular pain). Each item is scored by severity (0 = None to 3 = Very severe) multiplied by frequency (0 = Never to 4 = All 	King's PD Pain Scale score	Sum of severity x frequency for all 14 items. The KPPS score will be calculated as long as at least 13 questions have been answered. Missing values in a question will be replaced by the patient population's mean of the question, and rounded to an integer.	0 – 168/lower value desirable
the time) resulting in a subscore of 0 to 12.	Musculoskeletal Pain	Severity \times frequency for item 1	0 - 12/lower value desirable
	Chronic Pain	Sum of severity \times frequency for item 2 and 3	0 - 24/lower value desirable
	Fluctuation-related Pain	Sum of severity \times frequency for item 4 – 6	0 - 36/lower value desirable
	Nocturnal Pain	Sum of severity \times frequency for item 7 and 8	0 - 24/lower value desirable
	Oro-facial Pain	Sum of severity× frequency for item $9 - 11$	0 - 36/lower value desirable
	Discoloration, Oedema/Swelling	Sum of severity \times frequency for item 12 and 13	0 - 24/lower value desirable
	Radicular Pain	Severity x frequency for item 14	0 - 12/lower value desirable

32

